7.2.6. Final Visit (Visit 5; Day 14+/-1 day)

- FAAM-ADL (+/- 1 hour related to baseline assessment time whenever possible)
- Removal of the elastic bandage/semi rigid brace
- Ankle sprain-related measurements: VAS for evaluating pain at rest and on passive movement, (+/- 1 hour related to baseline assessment time whenever possible)
- Review of rescue medication usage recorded in the patient diary and transfer data into the eCRF
- Check other pain medication and/or RICE use with the patient (both are prohibited), record on medical records and enter into the eCRF if any
- Record any change in other concomitant medications
- Record use of arm crutches
- Evaluation and recording of any AEs the patient has experienced since the last visit including possible re-injury of the ankle. SAE evaluation and reporting if applicable
- Application of elastic bandage (if still required)/ semi-rigid brace
- Physical examination of cardiovascular, respiratory, musculoskeletal and gastrointestinal systems, head and eyes
- Measurement of body weight, blood pressure and heart rate
- Collection of Patient Diary used from Day 4 till Day 14
- Collect returned rescue medication and enter details into the eCRF
- Final drug accountability for rescue medication
- Collect answer from patients regarding their guess on which treatment they were receiving (Traumed[®] or diclofenac or placebo)
- Discuss further treatment and care with the patient according to the local medical practice.

8. Assessment of Efficacy

8.1. Primary Efficacy Parameter

Pain assessment on VAS for evaluating pain on passive movement

Ankle pain will be measured using a 100 mm VAS starting with no pain (0 mm) and ending with most severe imaginable pain the patient may imagine in relation to his/her ankle sprain (100 mm).

First the patients will be asked after 5 minutes rest to assess their pain themselves on a VAS scale for a secondary efficacy assessment (for details see section 8.2).

Then while the patient is still at rest the investigator should perform 10° dorsal- and 30° plantar flexion on the injured ankle and the patients will assess their pain themselves on a VAS scale (primary efficacy assessment). The range of movement will be controlled by using a goniometer. It is very important that no lateral move of the ankle joint will be made. The pain to be assessed is the pain on passive movement.

To ensure a consistent assessment between investigators, investigators will be trained together at the investigator meeting.

The date and time of assessment will be recorded. Pain assessments should take place +/- 1 hour related to baseline at each visit for the individual patient, whenever possible.

8.2. Secondary Efficacy Parameters

Pain assessment on VAS for evaluating pain at rest

Ankle pain will be measured using a 100 mm VAS starting with no pain (0 mm) and ending with most severe imaginable pain the patient may imagine in relation to his/her ankle sprain (100 mm).

The patients will be asked after 5 minutes rest to assess their pain themselves on a VAS scale.

Foot and Ankle Ability Measure (FAAM), Activities of Daily Living (ADL)

The FAAM is a validated questionnaire and was developed to meet the need for a self-reported evaluative instrument that comprehensively assesses physical function of individuals with musculoskeletal disorders of the leg, foot, and ankle.

It is a well-established and widely used responsive multidimensional outcome measure with a sensitivity capable of detecting subject-relevant symptoms and clinically significant changes in health in ankle sprain.

The FAAM-ADL/S consists of an ADL (21-item scale) and a sports (S) subscale (8 items) asking study participants to rate their ability to perform specific tasks. The FAAM-ADL/S is a valid and reliable instrument in the public domain (Martin 2005, Carcia et al. 2008).

The possible responses for each item are the following: no difficulty, slight difficulty, moderate difficulty, extreme difficulty, unable to do and not applicable.

In this clinical trial FAAM-ADL will be used. The scoring of the FAAM-ADL will be performed according to the recommendations of Martin et al. 2005.

The response to each item on the FAAM-ADL subscale will be recorded from 4 to 0, with 4 being 'no difficulty' and 0 being 'unable to do'. Responses marked as not applicable will not counted. The scores on each of the items will be added together to get the item score total. The total number of items with a response is multiplied by 4 will get the highest potential score. If all 21 items are answered, the highest potential score will be 84. If one item is not answered the highest potential score will be 80, if two are unanswered the highest potential score will be 76. The total item score will be divided by the highest potential score and then multiplied by 100 to produce the FAAM-ADL score that ranges from 0 to 100. According to the above recommendations the final scores of the FAAM-ADL subscale is to be standardized to a 0 - 100 scale (0 = worst score, 100 = best score).

Time to 50 % improvement of pain measured by VAS

The time to 50 % improvement will be calculated from VAS assessments on pain at rest performed at all patient visits using the percent changes from baseline (recorded at Day 1).

Rescue medication

The rescue medication use will be documented in the eCRF based on the information given in the patient diary and the drug accountability for rescue medication during the study.

8.3. Safety Assessments

In this study topical medications are applied for a local disorder where systemic effects are neither expected from the disorder nor from any of the investigational medications given. Due to these reasons, no safety laboratory testing is planned for this study.

Adverse Events

Definition, collection and reporting of adverse events are described in section 9.

Vital Signs

Vital signs (heart rate, systolic/ diastolic blood pressure) will be collected and evaluated by comparison of the results obtained pre- and post-treatment.

Physical examination

At screening/ baseline and at final visit a physical examination will be performed. Physical status of cardiovascular, respiratory musculoskeletal and gastrointestinal systems, head and eyes and in addition other abnormalities if applicable will be recorded in the eCRF.

Any clinically significant change observed at the final evaluation of vital signs and physical examination in comparison with baseline has to be evaluated carefully, recorded as AE if abnormal, and a possible causality will be evaluated (see section 9.3.2).

Appropriateness of Measurements

All clinical procedures that will be used in this study are standard and generally accepted.

9. Safety Reporting

9.1. Definitions

9.1.1. Adverse Events

An Adverse Event (AE) is any untoward medical occurrence in a patient or clinical investigation subject administered a pharmaceutical product and which does not necessarily have to have a causal relationship with this treatment.

An adverse event can therefore be any unfavourable and unintended sign (including an abnormal laboratory finding), symptom, or disease temporally associated with the use of an (investigational) medicinal product, whether or not considered related to the (investigational) medicinal product.

9.1.2. Serious Adverse Event

A serious adverse event (SAE) is any untoward medical occurrence that at any dose

- results in death
- is life-threatening (note: the term “life-threatening” refers to an event in which the patient is at risk of death at the time of the event; it does not refer to an event which hypothetically may cause death if it is more severe)
- requires patient hospitalisation or prolongation of existing hospitalisation (for the purpose of this study, a hospitalisation is defined as a hospital stay of at least 8 hours and/or an overnight stay)
- results in persistent or significant disability/incapacity

-
- is a congenital anomaly/ birth defect
- or
- other medically important condition.

Other medically important conditions are defined as important medical events that may not be immediately life-threatening or result in death or hospitalization but may jeopardize the patient or may require intervention to prevent one or more of the outcomes listed in the definition above. Examples of such events are intensive treatment in an emergency room or at home for allergic bronchospasm, blood dyscrasias or convulsion that does not result in hospitalisation, or development of drug dependency or drug abuse.

However, medical judgement has to be exercised in deciding whether an event is serious in any other situations considered medically relevant.

The evaluation of the AE as serious or not-serious is made independently of any attribution of causality.

Events requiring treatment on an emergency outpatient basis (not resulting admission to hospital) and not fulfilling any of the definitions of serious given above are NOT considered to be SAE.

9.1.3. Medical Events not to be Considered Adverse Events or SAEs

The following events should not be recorded as an AE/ SAE if recorded at the Screening/ Baseline Visit and/or the basic examination of a clinical trial:

- A pre-planned procedure, e.g. surgery and invasive procedures, unless the condition for which the procedure was planned has worsened since baseline. Complications to pre-planned procedures should be recorded as AEs.
- A pre-existing condition found as a result of Screening/ Baseline Visit procedures.
- Variations in chronic disease symptoms and in related investigational results if similar variations were observed earlier. These include symptoms and their intensity that are requested and documented in the eCRF, Diary or Questionnaire at the respective visits.
- Compromised or biologically implausible test results, e.g. mechanical or physical effects on blood samples or values incompatible with life, respectively.
- Pregnancy is not considered to be an AE.

Note: Any worsening in severity or frequency of a concomitant illness or any new illness diagnosed in the study period has to be regarded as AEs/SAEs.

In this clinical trial deterioration of ankle sprain symptoms will not be recorded as an AE/SAE.

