5.3.3. Discontinuation of Treatment

Patients who meet any of the discontinuation criteria will discontinue investigational treatment and will be followed up only for AEs until Day 14.

Study investigators may request the patient to discontinue investigational treatment in case of:

- Diagnosis of Grade 3 ankle sprain
- Any other medical condition requiring in the opinion of the investigator a change of the therapy for the baseline condition
- Occurrence of a medical condition requiring use of prohibited medications or treatment
- Medical condition affecting assessment of the primary endpoint
- Medical conditions affecting patient safety if the investigational therapy is continued: conditions and AEs causing safety concerns with investigational treatment to the ankle

joint area OR any other AE or condition that - in the opinion of the investigator – endangers patient safety if the investigational therapy is continued

- Lack of efficacy as considered by the investigator.

Discontinuation of investigational treatment and its reason will be documented in the medical records and recorded in the eCRF. If a patient discontinues investigational treatment, the discontinuation of treatment visit should be performed. Further treatment of the ankle sprain will be at discretion of the investigator and will not be recorded in the eCRF. In case the patient will be treated in another hospital or practice, the investigator will make efforts to collect and record AEs the patient might have had until Day 14. This can be done during an onsite visit or a phone call with the patient or with the treating physician at the other hospital or practice. Patients who discontinue prematurely from the study will not be replaced, except patients with Grade 3 sprain confirmed at any day up to Day 4 ('replacement' referring to the total number of patients to be enrolled, see also definitions in section 11.4).

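### Section 9.1.3 exempts worsening sprain symptoms from SAE as well as AE recording with no exception for serious events, and early stoppers' later worsening has no recording route

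*Protocol*

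**What the plan says.** Protocol 9.1.3 lists findings that are not to be recorded as AEs or SAEs. After the list comes a note that keeps other conditions reportable: "Any worsening in severity or frequency of a concomitant illness or any new illness diagnosed in the study period has to be regarded as AEs/SAEs". A separate closing sentence then deals with the study condition: "In this clinical trial deterioration of ankle sprain symptoms will not be recorded as an AE/SAE".

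Protocol 9.1.2 defines an SAE as any untoward medical occurrence meeting one of several criteria, among them that it "requires patient hospitalisation or prolongation of existing hospitalisation" or "results in persistent or significant disability/incapacity".

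Protocol 8.3 requires a clinically significant change at the final physical examination, which covers the musculoskeletal system, to be recorded as an AE if abnormal.

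Under protocol 5.3.3, patients who discontinue treatment "will be followed up only for AEs until Day 14". The section adds: "Further treatment of the ankle sprain will be at discretion of the investigator and will not be recorded in the eCRF". It also provides: "Discontinuation of investigational treatment and its reason will be documented in the medical records and recorded in the eCRF", and calls for a discontinuation visit. By the heading of 7.2.5, that visit follows the Visit 4 procedures, including VAS and FAAM-ADL.

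**The concern.** Keeping ordinary symptom fluctuation out of the AE data is common and reasonable when the efficacy scales measure the same thing. That justification has two limits here.

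First, a VAS or FAAM-ADL score does not record an admission or a lasting disability as a safety event. If a worsening reaches that level, only the SAE route would document it, and 9.1.3 read literally closes that route. An exempt event also skips the causality question in 9.3.2, so nobody is asked whether the gel contributed.

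Second, the justification requires the scales to be still in use. For early stoppers they end with the discontinuation visit. Lack of efficacy is itself a discontinuation reason in 5.3.3, so this group may include patients who are doing badly, and its make-up may differ between arms. That is inference; the documents give no rates.

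Tolerability and safety of the test gel are a stated objective, and the treated site is the sprained ankle.

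**Working it through.** The point rests on reading the rules together. The one safety figure in the plan is checked at the end.

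**Step 1: does anything in 9.1.3 limit the exemption to non-serious events?** No. The sentence names AE and SAE together. Elsewhere in the section the drafters did write limits: a pre-planned procedure is exempt unless its underlying condition has worsened, and the note retains worsening of concomitant illness. The sprain sentence has no such limit. The sprain is the study condition, so the note on concomitant or new illness does not bring its symptoms back.

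**Step 2: compare with 9.1.2 and 8.3.**

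| Event | 9.1.3 | Other rule |
|---|---|---|
| Sprain symptoms worsen, patient admitted | Not recorded | SAE (9.1.2) |
| Sprain symptoms worsen, lasting disability | Not recorded | SAE (9.1.2) |
| Significant abnormal musculoskeletal change at final examination, due to the sprain | Not recorded | AE (8.3) |

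No order of precedence is given.

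**Step 3: where is symptom worsening captured?**

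- Completers: VAS, FAAM-ADL, rescue medication review and a physical examination at Day 14 (7.2.6).
- Early stoppers, up to the stop: the reason in the eCRF, plus VAS and FAAM-ADL at the discontinuation visit (5.3.3, 7.2.5).
- Early stoppers, afterwards: AE follow-up only (5.3.3). Symptom worsening is not an AE (9.1.3), later sprain treatment is not recorded, and no further VAS is planned. No route remains.

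If the discontinuation visit is on Day d, the uncovered period is 14 − d days: 14 − 2 = 12 from Day 2, and 14 − 4 = 10 from Day 4. Under LOCF (protocol 11.1.4, SAP 9.5.1.2) the last earlier value stands in for this period, so later worsening would not appear in the efficacy results either.

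Patients withdrawn from the study, including those regraded to Grade 3 by Day 4, have no further assessments under separate rules (5.3.4, 7.2.4). Changing 9.1.3 alone would not alter that.

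**Step 4: the safety sample size (protocol 11.4).** Inputs: incidence 1%, detection probability 95%, 4% drop-out.

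- n = ln(0.05)/ln(0.99) = 298.07, rounded up to 299. Check: 1 − 0.99^299 = 0.9505.
- 299/0.96 = 311.5, rounded up to 312.
- With the enlarged arm of 404: 1 − 0.99^404 = 0.983.

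Both planned figures reproduce. They hold only for events that the protocol allows to be recorded as AEs, so they give no assurance about exempt sprain worsening.

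**The case against.** The strongest reply is that the protocol captures a good deal, and most of that reply stands.

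- A reader might infer that worsening is captured nowhere once treatment stops. The documents do not support this. Completers have a full sprain assessment at Day 14, and the worsening that makes a patient stop is documented through the recorded reason and the discontinuation visit.
- A reader might infer that local reactions to the gel can vanish as sprain worsening. The protocol says repeatedly that AEs at the application site are to be recorded (Table 1 footnote 4; 7.2.2 to 7.2.5; 9.2), and 9.3.2 tells the investigator to assume a possible relationship when one cannot be excluded. Misclassification is conceivable, but it would run against explicit instructions.
- A reader might infer that no serious case would ever be reported. That goes too far. The exemption covers symptoms. A new illness stays reportable, and AE evaluation at Visits 2 to 5 covers events "since the last visit including possible re-injury of the ankle". If care moves elsewhere, the investigator must try to collect AEs until Day 14. The supportable statement is that a serious symptom worsening need not be reported on a literal reading.

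The population also limits the problem: Grade 1 or 2 outpatients, with diagnoses requiring hospitalisation, surgery or a cast excluded at entry.

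None of this supplies the missing seriousness exception, says which section prevails, or gives early stoppers a recording route after the discontinuation visit. The 8.3 rule does not help them, because it operates at the final examination and they are followed only for AEs.

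**Conclusion.** The concern holds in two parts. First, 9.1.3 conflicts with 9.1.2 on serious worsening of sprain symptoms and sits badly with 8.3 on the final examination. Second, for early stoppers, symptom worsening between the discontinuation visit and Day 14 is recorded neither as an AE nor as an efficacy measurement.

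The size cannot be computed, because the documents give neither the number of early stoppers nor the frequency of serious worsening. SAP 9.5.1.2 describes missing efficacy values as marginal in number, which suggests that few patients are affected by the second part. Serious cases are probably few under the first. The matter still deserves correction because it concerns serious-event reporting in a trial with a safety objective. It does not bear on the confirmatory tests directly.

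The conclusion assumes that investigators apply 9.1.3 as written and that no other study document, such as a safety manual, resolves the conflict.

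**What to change.** Reconcile protocol 5.3.3, 8.3, 9.1.2 and 9.1.3:

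- In 9.1.3, limit the exemption to non-serious changes in sprain symptoms that are captured by VAS or FAAM-ADL at a study visit.
- State that worsening which meets any criterion in 9.1.2 is reported as an SAE.
- State that worsening in an early stopper after the last VAS is recorded as an AE during the existing follow-up to Day 14.
- Make the 8.3 rule on the final examination consistent with the revised exemption.

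No new visit is needed. The cost is a few extra AE forms and a protocol amendment. If the amendment is substantial, 1.4 requires approval by the coordinating investigator, sponsor, authority and ethics committee, so it takes more than editing a sentence.

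SAP section 7 records a hard-lock transfer on 29 March 2021. If data collection is closed, the report should state that sprain-symptom worsening was outside AE and SAE recording, including after early discontinuation, and should tabulate the recorded discontinuation reasons by arm. The end-of-treatment tables in SAP 13.3.1 are a natural place for this.

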9.1.4. Adverse Reaction

An Adverse Reaction (AR) is any untoward and unintended response to an IMP that is considered to have a reasonable possibility of a causal relationship with the treatment, i.e. the relationship cannot be ruled out.

9.1.5. Unexpected Adverse Reaction

An unexpected adverse reaction is an adverse reaction, the nature or severity of which is not consistent with the information available on the IMP reference safety information, (i.e. the actual IB for an unauthorized IMP; an SmPC/ CCSI/ CCDS for an authorized product.

9.1.6. Suspected Unexpected Serious Adverse Reaction

A suspected unexpected serious adverse reaction (SUSAR) is a serious AR, the nature or severity of which is not consistent with the applicable reference safety information, (i.e. the actual IB for an unauthorized IMP; an SmPC/ CCSI/ CCDS for an authorized product.

9.2. Recording of Adverse Events

All AEs that occur during the entire course of the study after the patient has signed the informed consent are to be collected and reported in the eCRF, regardless of whether they are reported by the patient, elicited by investigator questioning, detected through physical examination, or by other means. These should include AEs observed at the site of administration of the IMP (lateral ankle) as well. AEs of Screening Failures will be documented on the paper *AE Reporting Form* as they will not be entered in the eCRF.

9.3. Evaluation of Adverse Events

As far as possible, each AE is described by:

- duration (start and end dates)
- start/end of investigational medication and/or non-investigational medication including – but not limited to – rescue medication
- intensity (mild, moderate, severe)
- investigator causality (relationship to the investigational medicinal product)

-
- action(s) taken (dose change of investigational medication and/or non-investigational medication including – but not limited to – rescue medication, treatment of AE etc.) including start and end of respective action
 - concomitant diseases and respective medication in general
 - start, end and dosage of rescue medication
 - outcome.

9.3.1. Adverse Event Intensity

AE intensity determined by the clinical investigator on the basis of his/her direct observations or the patient's reporting:

- Mild: causes no limitation of usual activities; the patient may experience slight discomfort
- Moderate: causes some limitation of usual activities; the patient may experience annoying discomfort
- Severe: causes inability to carry out usual activities; the patient may experience intolerable discomfort or pain.

9.3.2. Adverse Event Causality (Relationship Guide)

Any AE has to be judged for causality (relationship to investigational medication and/or to non-investigational medication including – but not limited to – rescue medication and relationship to study procedure). The investigator will assess causal relationship between IMP and all AEs whether there is a reasonable possibility that the investigational medication caused the event.

The assessment will be based on the question 'Do you consider that there is a reasonable possibility that the AE may have been caused by the IMP?'

The evaluated answer will be 'yes' or 'no'.

In case the reasonable possibility can't be excluded, reasonable possibility of causal relationship should be considered until further evidence will be available to exclude it.

For AEs the causal relationship to other medications and study procedures will also be assessed. In case of reasonable possibility that the AE may have been caused by study procedures or other medication the evaluated answer will be 'yes'.

